13.11 Study Stopping Rules

The study may be discontinued prematurely in the event of any of the following:

- A life-threatening AE that is possibly or probably related to treatment.
- A fatal AE that is possibly or probably related to treatment.
- New information leading to unfavorable risk-benefit judgment of the study drug.
- Sponsor's decision that continuation of the trial is unjustifiable for medical or ethical reasons.
- Discontinuation of development of the Sponsor's study drug.

Health Authorities and IRB will be informed about the discontinuation of the study in accordance with applicable regulations. The study may be terminated or suspended on request of Health Authorities or Sponsor.

14. Discontinuation and Replacement of Patients

14.1 Definition of Study Completion

A patient who completes visits through the Day 225 (± 3) visit will be recorded as having completed the double-blind period of the study.

A patient who completes visits through the Day 176 (± 3) visit and enters into the OLE period of the study will be categorized as having completed the double-blind period of the study.

A patient who completes visits through OLE Day 197 (Day 372) (± 3) visit will be recorded as having completed the OLE period of the study.

14.2 Early Discontinuation of Study Drug

A patient may be discontinued from study treatment at any time if the patient, the Investigator, or the Sponsor feels that it is not in the patient's best interest to continue. The following is a list of possible reasons for study treatment discontinuation:

- Patient withdraws consent.
- An AE that, in the opinion of the Investigator, results in it being in the best interest of the patient to discontinue study treatment.
- Protocol deviation requiring discontinuation of study treatment.
- Participation in any other study during the duration of this study.

- Use of a non-permitted concomitant drug which may adversely affect data interpretation in the opinion of the Medical Monitor.
- Loss of ability to freely provide consent through imprisonment or involuntary incarceration or treatment of either a psychiatric or physical (e.g., infectious disease) illness.

If a patient is withdrawn from treatment due to an AE, the patient will be followed and treated by the Investigator until the abnormal parameter or symptom has resolved or stabilized.

All patients who discontinue study drug treatment should be encouraged to continue on study and complete assessments and procedures according to the 12-week follow-up period in [Table 2](#), if possible (including follow-up EGD with colonoscopy).

Reasonable attempts will be made by the Investigator to provide reasons for patient withdrawals. The reason for the patient's withdrawal from the study or all attempts to acquire such, will be specified in the source documents.

15. Statistical Methods and General Considerations

This section outlines the statistical methods to be used for the analysis of the data from the study. A separate Statistical Analysis Plan (SAP), which must be documented as completed prior to unblinding the study, will describe data handling and statistical techniques in full detail and will supersede the statistical methods detailed in the protocol. The SAP will detail any modifications to the analysis plan described below.

Unless specified otherwise, baseline will be defined as the last 2 weeks of observation before the first intravenous infusion of the study drug. All patient data will be listed. When appropriate, summary statistics of number of non-missing values, mean, median, standard deviation, minimum, and maximum will be computed for continuous variables, and summary statistics of number and proportion will be computed for categorical variables. Two-sided 95% confidence intervals will be provided for the mean and proportion. No formal statistical inferences will be made for safety parameters.

15.1 Sample Size

A total of approximately 80 patients will be enrolled.

First Co-Primary Endpoint: A sample size of 40 patients per treatment group will have >90% power to demonstrate a greater proportion of histologic responders at Week 24 in AK002 patients when compared to placebo patients, assuming the proportions of histologic responders are 0.6 and 0.1 in the AK002 and placebo groups, respectively.

Second Co-Primary Endpoint: A sample size of 40 patients per treatment group will provide 80% power to detect a statistically significant difference of 7.4 points between AK002 and placebo in the mean reduction from baseline in TSS at Weeks 23–24, assuming a common standard deviation of 12.5 points([AK002-003](#) data on file).

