The pattern-mixture model will be implemented using multiple imputations, and the inference of this sensitivity analysis will be based on the combined estimates using the standard multiple imputation technique. The imputed data sets will be analyzed with the same MMRM model utilized in the primary analysis and then summarized using PROC MIANALZE. The other is to analyze the average of Week 23 through Week 24 using ANCOVA with treatment and study site (with pooling by geographic location) as factors, gender and baseline TSS (continuous) as covariates. Missing Week 23 through Week 24 weekly TSS will be imputed prior to ANCOVA using SAS PROC MI under the MAR assumption. Detailed specifications for the missing data imputation will be provided in the SAP.

Analysis of binary secondary endpoints will be based on the CMH test stratified by the randomization stratification factor (baseline TSS <28 vs \geq 28).

Change from baseline in continuous secondary outcomes measured at multiple post-baseline time points will be analyzed longitudinally using MMRM techniques. The model will include fixed effects for baseline value, treatment, week, treatment by week interaction, baseline value by week interaction, and allow for random subject effects. The model variance-covariance matrix will be unstructured. However, if computation does not converge, the matrix will take the form of Toeplitz, AR(1), and compound symmetry, whichever converges first. The Kenward-Rogers approach for computing denominator degrees of freedom will be used to account appropriately for pooling of within-subject and between-subject variance estimates. Least square means and the 95% CI for the between group difference will be estimated for each week.

To control for the overall false-positive error rate, the hypothesis testing for the primary and secondary endpoints using the Evaluable population in the subgroup defined above as the only population for primary inference are ordered as follows:

- The 2 co-primary efficacy endpoints will each be tested 2-sided at $\alpha=0.05$ level. If both tests are statistically significant, the hypothesis tests for the secondary endpoints will proceed sequentially based on the order specified in Section 4.2.

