Approximately 40% of patients had concomitant EoE. In those patients, a mean reduction of 95% of eosinophils/hpf in esophageal biopsies for AK002-treated patients was observed vs no change for placebo-treated patients. Also, 13 of 14 AK002-treated patients (93%) were histologic responders as defined by ≤ 6 eosinophils/hpf vs 1 of 9 placebo-treated patients (11%). Dysphagia improved by 53% in AK002-treated patients vs 17% in placebo-treated patients.

More than 90% of patients in the Phase 2 study elected to continue into a long-term continuation study. In that study, a starting dose of 1 mg/kg was used, followed by subsequent doses of 3 mg/kg. Premedication of 80 mg prednisone was administered the day before the first and second dose for 20 of the 58 patients dosed. Using this premedication regimen, no IRR were observed with the first infusion in the extension study.

Study AK002-016 was a Phase 3, randomized, double-blind, placebo-controlled study of lirentelimab in subjects with moderate-to-severe EG/EoD. The study enrolled 180 subjects with EG and/or EoD. Subjects were required to be moderately to severely symptomatic based on a patient reported symptom questionnaire and to have biopsy-confirmed eosinophilia of the stomach (≥ 30 eosinophils/hpf in 5 hpf) and/or duodenum (≥ 30 eosinophils/hpf in 3 hpf). Subjects were randomized 1:1 to receive a monthly infusion of placebo or 1 mg/kg lirentelimab IV for the first month followed by 5 doses of 3 mg/kg lirentelimab administered monthly. Disease symptoms were measured daily using a patient-reported outcome (PRO) questionnaire (TSS6) that scored 6 symptoms (abdominal pain, nausea, bloating, early satiety, abdominal cramping, and loss of appetite), each on a scale from 0 to 10. Co-primary endpoints were the proportion of responders with ≤ 4 eosinophils/hpf in 5 hpf in the stomach and/or ≤ 15 eosinophils/hpf in 3 hpf in the duodenum at the end of Week 24, and the absolute change from baseline in TSS6 at Weeks 23–24. Subjects who completed Study AK002-016 had the option to receive lirentelimab in Study AK002-016X, an open-label extension (OLE) study.

[figure not shown]
In this Phase 3 study, lirentelimab showed a statistically significant benefit compared to placebo on the histology co-primary endpoint but did not achieve statistical significance on the subject reported symptomatic co-primary endpoint ([Table 1](#)).

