4.5.1 Population Targeted by the Scientific Question

The population targeted by the scientific question is defined by the inclusion and exclusion criteria as part of the study protocol. Patients must have a histological diagnosis of EoD. A key aspect of eligibility is that subjects must have a weekly average score of abdominal pain, nausea, or diarrhea ≥ 3 on the PRO questionnaire (score from 0–10) for at least 2 weeks of screening and a weekly average TSS of ≥ 10 for at least 2 weeks of screening. It is noted that history of inflammatory bowel disease, other chronic inflammatory diseases in the colon (with the exception of eosinophilic colitis), celiac disease, achalasia, or esophageal surgery is an exclusionary measure in the study. Supplementary analysis of data from the AK002-016 study focused on identification of baseline characteristics, which correlate with degree of change in TSS6 at Weeks 23–24. This examination identified 8 variables (age, gender, duodenal eosinophil counts, diarrhea frequency, history of IBS, abdominal pain, >6 esophageal eosinophils/hpf, and history of IBS in combination with diarrhea intensity ≥ 3) that most influenced the degree of change of the TSS6 endpoint. Two of the variables (>6 esophageal eosinophils/hpf and history of IBS in combination with diarrhea intensity ≥ 3) potentially reflect other disease states (IBS, GERD, or even active EoE) that could potentially impact multiple symptom components of TSS6. To ensure these 2 variables do not compromise the capacity to detect the treatment effect with symptoms of EoD as measured by the TSS6 questionnaire, the primary comparison of AK002 vs placebo will be conducted only on the Evaluable population defined as patients who do not meet any of the following criteria:

- 1) >6 eosinophils/hpf in at least 1 esophageal site at baseline.
- 2) Documented history of irritable bowel syndrome and baseline diarrhea intensity ≥ 3 .

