- Prior EGD and colonoscopy biopsy samples may be used for eligibility as long as they were performed within 45 days of the screening window for the AK002-021 study and were performed and centrally assessed using the same criteria as for the AK002-021 study.
- If patients meet histology and symptom eligibility criteria, they will be randomized and stratified by the highest weekly mean TSS of disease activity recorded during the screening period (<28 or \geq 28 strata). The IRT will assign patients 1:1 to receive 6 doses of AK002 or placebo.
- Pre-study medications and dietary restrictions should remain unchanged throughout the screening period and throughout the study. Systemic or topical corticosteroids above 10 mg prednisone daily (or the equivalent thereof) will not be allowed, except as a premedication prior to the first infusion only, to treat an IRR that occurs during infusion, or the use is due to unforeseen circumstances when it is deemed medically necessary to treat an unrelated medical condition.
- Eligible patients will receive the first dose of placebo or AK002 (3 mg/kg) on Day 1 with premedication of 80 mg oral prednisone 12–24 hours prior to the start of the infusion.
- If the study drug is well tolerated (no stopping rules being met), patients will receive additional doses of placebo or AK002 (3 mg/kg) on Days 29, 57, 85, 113, and 141. With the exception of Day 1, steroid premedication will only be allowed with the written approval of the Medical Monitor.
- Patients will remain at the site for at least 1 hour of observation following the end of the infusion.

- A repeat EGD and colonoscopy with biopsy will be performed on Day 169 (± 3) or 28 (± 3) days after last dose of study drug if patient early-terminates from the study (between the Day 29 visit and the Day 169 visit).
- Daily administration of the PRO questionnaire (including additional questions) throughout the study and the follow-up period for all patients.
- Patients will rate their impression of disease severity **CCI** [REDACTED] and disease improvement **CCI** [REDACTED] at specified time points during the study.
- Patients will be prompted to answer additional questions about dysphagia and constipation on a daily basis during screening and throughout the study. These will be completed following the PRO questionnaire.

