### 3.5 Determination of Sample Size

A total of approximately 80 subjects will be enrolled.

**First Co-Primary Endpoint:** A sample size of 40 subjects per treatment group will have >90% power to demonstrate a greater proportion of histologic responders at Week 24 in AK002 subjects compared to placebo subjects, assuming the proportions of histologic responders are 0.6 and 0.1 in AK002 and placebo groups, respectively.

**Second Co-Primary Endpoint:** A sample size of approximately 40 patients per treatment group will provide 80% power to detect a statistically significant difference of 7.4 points between AK002 and placebo in the mean reduction from Baseline in TSS at Weeks 23-24, assuming a common standard deviation of 12.5 points (AK002-003 data on file).

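### The stated 80% power for the TSS co-primary does not follow from its own inputs, which give about 74% at 40 per arm and less in the Evaluable population where the test is done

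*Protocol*

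**What the plan says.** Protocol 15.1 concludes for the second co-primary: "A sample size of 40 patients per treatment group will provide 80% power to detect a statistically significant difference of 7.4 points". The outcome is the fall in TSS from baseline to Weeks 23–24, and the SD is taken as 12.5 in both arms, from study AK002-003. The synopsis gives the same statement. SAP 3.5 has it with one softening word: "A sample size of approximately 40 patients per treatment group will provide 80% power".

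The other inputs are also explicit. On the level, the synopsis (Statistical Analysis) says: "The 2 co-primary efficacy endpoints will each be tested 2-sided at $\alpha=0.05$ level". SAP 5.8 agrees. On allocation, Protocol 5.1 says: "The IRT will assign patients 1:1 to receive 6 doses of AK002 or placebo". The total is about 80 patients, described as enrolled (Protocol 15.1), dosed (7.1) and randomized at about 40 to each arm (10.2).

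The confirmatory test does not use all of these patients. Protocol 4.5.1 says "the primary comparison of AK002 vs placebo will be conducted only on the Evaluable population". Protocol 15.2 and SAP 6.1.5 define that population by removing treated patients who at baseline have more than 6 eosinophils/hpf in an esophageal biopsy, or a documented IBS history together with diarrhea intensity of 3 or more. Under Protocol 15.6.1, TSS data from patients with an intercurrent event before the end of Week 24 are set to missing. Neither document gives an expected Evaluable share, a dropout rate or an inflation of the sample size.

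**The concern.** Two things look wrong. First, the standardized difference is 7.4/12.5 = 0.592, and 40 per arm is too few to give 80% power at that size. Second, the 40 per arm in the calculation is the number enrolled, but the primary test is run on a subset of them, so the calculation does not describe the test that will be done.

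This endpoint decides the trial. Secondary testing opens only if both co-primaries are significant, and histology has ample power. Protocol 2.3 reports that the earlier Phase 3 study, AK002-016, met its histology co-primary and missed its TSS co-primary. If the stated power is too high, the chance of success is overstated, and a null TSS result would be read against a power the design did not have.

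**Working it through.** **Inputs.** Difference 7.4, common SD 12.5 and n = 40 per arm (Protocol 15.1); two-sided alpha 0.05 (synopsis; SAP 5.8); 1:1 allocation (Protocol 5.1).

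**Attempt to reproduce 80%.**

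- Standard error of the difference: 12.5 × √(2/40) = 2.795.
- Noncentrality: 7.4 / 2.795 = 2.648.
- Normal approximation: Φ(2.648 − 1.960) = Φ(0.688) = 75.4%.
- Two-sample t-test (noncentral t, 78 df, critical value 1.991): 74.4%.
- One-sided 0.05 would give 83.6% (t) or 84.2% (normal), so sidedness does not explain the figure either, and it would contradict the plan.

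**What 80% would take, changing one input at a time.**

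- Sample size, normal approximation: n = 2 × (1.960 + 0.842)² × 12.5² / 7.4² = 44.8, so 45 per arm. By the t-test, 45 per arm gives 79.3% and 46 gives 80.2%, so 46 per arm (92 in total).
- Difference at 40 per arm: 7.93 (t) or 7.83 (normal).
- SD at 40 per arm: 11.67 (t) or 11.81 (normal).
- Expressed as covariate adjustment: 1 − (11.67/12.5)² = 0.129. Covariates would have to explain about 13% of the variance, a correlation of about 0.36.

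**Evaluable subset.** The excluded share f is not stated, so it is an assumption here. The number per arm is 40 × (1 − f), with the difference and SD held at 7.4 and 12.5. The last column is 92/(1 − f), rounded up.

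| Excluded share (assumed) | Evaluable per arm | Power (t-test) | Randomized total for 92 Evaluable |
|---|---|---|---|
| 0% | 40 | 74.4% | 92 |
| 10% | 36 | 69.8% | 103 |
| 20% | 32 | 64.5% | 115 |
| 30% | 28 | 58.5% | 132 |
| 40% | 24 | 51.9% | 154 |

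For scale only: of the Phase 2 study's 65 patients, Protocol 2.3 says "Approximately 40% of patients had concomitant EoE", and it reports esophageal response for 14 + 9 = 23 of them (35%). At 35% excluded, 26 per arm would remain and power would be 55.3%.

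**Share of the joint requirement.** Fisher's exact test for 0.6 versus 0.1 has 99.8% power at 40 per arm and about 97% at 26 per arm, so the plan's claim of more than 90% for histology is correct. At 40 per arm the probability that both tests succeed is at least 74.4% + 99.8% − 100% = 74.2% and at most 74.4%, so TSS power is in effect the trial's power.

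**The case against.** The strongest reply is that the planned analysis is not an unadjusted t-test. It is an MMRM with baseline TSS, gender and pooled site. If 12.5 is the unadjusted SD and a covariate correlates about 0.36 with the outcome, power at 40 per arm is 80%. That is plausible, and it could explain the figure. But the documents state neither the test behind the calculation nor any reduction of the SD, so the 80% cannot be obtained from what is written. The explanation would also leave the Evaluable exclusions uncovered: at 32 per arm the covariates would need to explain about 31% of the variance, and at 26 about 44%.

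Three further points limit how the subset figures can be used, and they stand:

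- The table holds the effect and SD constant. The Evaluable population was chosen because the excluded features were thought to obscure the treatment effect, so the effect or SD in it might be more favourable.
- The Phase 2 share transfers poorly. That study enrolled EG and/or EoD and counted concomitant EoE. This trial enrols EoD without EG, uses a threshold of more than 6 eosinophils/hpf, and takes esophageal biopsies only in selected patients.
- Data set to missing after an intercurrent event are not a complete loss, because the MMRM keeps the earlier visits.

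It can also be said that Protocol 10.2 calls 80 a minimum. The same section still puts about 40 in each arm and gives no Evaluable target. Finally, planning power changes no estimate, test or error rate. That is true, but it does not make the stated figure correct.

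**Conclusion.** The concern holds. With the plan's own difference, SD, sample size and two-sided level, power is 74.4% (75.4% by the normal approximation), not 80%. The shortfall is about 5 to 6 percentage points, or 6 patients per arm, which is more than rounding. This part rests on reading 12.5 as the SD that applies to the comparison; a documented covariate-adjusted SD of about 11.7 would remove the discrepancy at 40 per arm.

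Separately, the calculation uses the number enrolled while the primary test uses the Evaluable subset. With the plan's effect and SD, any exclusion takes power below 74%. The size of that loss is unknown because the excluded share is not stated. Between 10% and 40% excluded, power falls from 69.8% to 51.9%, assuming an unchanged effect and SD and no other loss of data.

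**What to change.** Correct the synopsis, Protocol 15.1 and SAP 3.5 together:

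1. State about 74% power for 7.4 points at 40 Evaluable patients per arm, or 80% power for 7.93 points (7.9 gives 79.7%). If the 80% relied on covariate adjustment, state the adjusted SD or the assumed correlation and its source.
2. Say that the calculation refers to Evaluable patients. Give the expected Evaluable number per arm and the power at that number. Both exclusion criteria are baseline variables, so the total can be counted without unblinding and halved for 1:1 allocation.
3. State the allowance made for data set to missing after intercurrent events, or that none is made.

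The cost is wording only. Enrolment, endpoints and analysis stay as they are; the stated power becomes less favourable. If the sponsor wants 80% power under the stated inputs, the target is 46 Evaluable patients per arm, with enrolment raised for the expected non-Evaluable share, but this correction does not require it.

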15.2 Analysis Populations

The Safety population is defined as all patients who are randomized and have received at least 1 infusion of the study drug.

The primary efficacy analysis population is the Evaluable population defined as all randomized patients who have received at least 1 infusion of the study drug and at study entry do not meet any of the following criteria:

- 1) >6 eosinophils/hpf in at least 1 esophageal biopsy at baseline.
- 2) Documented history of irritable bowel syndrome and baseline diarrhea intensity ≥ 3 .

The complement to the Evaluable population will be referred to as the Excluded population. The Per Protocol (PP) population, defined as Evaluable population patients who have received at least 1 infusion of study drug and did not have significant protocol violations possibly interfering with assessment of efficacy. The Evaluable and Excluded populations will be used for all efficacy analysis. The PP population will be used for the primary endpoints and select secondary endpoint analyses. The Safety population will be used for all safety analysis.

The study statistician along with the study team will review protocol deviations to identify patients to be excluded from the PP analysis population.

15.3 Patient Disposition

Patient disposition and reason for early discontinuation will be tabulated. Patient demographics, baseline characteristics, and treatment exposure will be summarized.

